#### 6.1.2 *Randomization and Masking*

A block randomization code will be independently computer-generated by the Clinical Trial Services at SHSC and remain locked in a secure location in that department. Kits with study medication will be consecutively pre-packaged as per randomization sequence prior to commencement of the trial. All study personnel will remain blind to treatment allocation and block size until the final patient has completed follow-up and the database is locked. Unblinding will not be allowed unless there exists exceptional clinical circumstances that justify it, such as if acute medical management of an SAE is required. Individuals performing study related measures (e.g., plasma analyses, imaging analyses) will also remain blind to treatment allocation and all clinical data throughout the entire duration of the study.

#### 6.1.3 *Receiving and Storage*

##### 6.1.3.1 Receipt of Investigational Product

SISU will ship the investigational product to the Pharmacy Department at SHSC and will provide the qualified investigator with chain of custody documentation as well as certificates of analysis.

Upon receipt of the investigational product, the Pharmacy will count and verify that the shipment contains all the items noted in the shipment inventory. Any damaged or unusable product in a given shipment will be documented in the study files and study staff will be informed.

SISU will ship the empty capsule shells to the Pharmacy Department at SHSC and will provide the qualified investigator with chain of custody documentation as well as certificates of analysis. Upon receipt of the empty capsule shells, the Pharmacy will count and verify that the shipment contains all the items noted in the shipment inventory. Any damaged or unusable capsules will be documented in the study files and study staff will be informed.

#### **6.1.3.2 Storage and Stability**

The investigational product will be stored in a secure location in a temperature monitored area at Sunnybrook Health Sciences Centre. There are no special handling requirements for storing NAC.

#### ***6.1.4 Participant Compliance Monitoring***

Compliance will be monitored using capsule counts (non-compliance is defined as taking < 80% of their capsules). Study participants will not be withdrawn from the study for non-compliance unless the PI/QI have safety concerns.

### 7.2 MRI SCAN

The MRI will be performed on a 3 Tesla scanner at screening 2 visit to determine baseline WMH severity. We will use the standardized Canadian Dementia Imaging Protocol, which allows for semiautomatic and simultaneous quantification of regional small vessel disease, including WMH, lacunes, and perivascular spaces, as well as cerebrospinal, grey and white matter segmentation. Sequences include high resolution 3D T1, Proton Density (**PD**)/T2 weighted sequence, fluid attenuated inversion recovery (**FLAIR**), Susceptibility Weighted Imaging (for microbleed counts). The PD/T2 images will be used for image co-registration and to generate intracranial volume mask. Following tissue segmentation, regional parcellation of 26 bilateral brain regions will be generated using Semiautomatic Brain Region Extraction (**SABRE**; Sunnybrook Health Sciences Centre). FLAIR or PD/T2 images will be used to identify WMH using one of two semiautomatic protocols (Fuzzy Lesion Extractor [**FLEX**] or Lesion Explorer with manual selection editing to obtain reliable quantification of the number, size, location, and volume of WMH lesions. All image acquisition, processing, and scoring will be blinded to clinical information using our standardized protocol.

### 7.2.1 MRS Data Acquisition

MRS data will be acquired to assess GSH concentrations in vivo. The regions of interest in the brain will be chosen based on a high-quality signal and relevance to the cognitive assessments outlined in section 7.1. The MEGA-PRESS pulse sequence will be used, enabling expression of GSH levels as an absolute concentration in mM.

## 7.3 Blood Samples

Blood samples will be collected (schedule shown in Appendix A) to measure plasma levels of GSH antioxidant system and serum levels of lipid peroxidation as previously described . Briefly, approximately four teaspoons of blood will be collected by antecubital venipuncture from each study participant following at least 12 hours of fasting. Blood draws will be scheduled for 0900 h  $\pm$  3 h to minimize the effect of diurnal or dietary variation on marker concentrations. Blood will be drawn into SST and EDTA-containing vacutainer tubes and centrifuged (The Drucker Company; Model 614B) at 1000 x g for 10 minutes. Plasma and serum will be isolated and frozen at -80 C. Stored samples will be batched for analysis. **GSH antioxidant system:** We will measure levels of GPx, GR and GST using standard western blotting technique with appropriate primary and secondary antibodies. **S100B Assay:** We will measure levels of S100B (pg/mL) using a standard sandwich immunoassay (ELISA). **LPH Assay:** Early-stage oxidative damage to lipids will be evaluated by measuring the levels of LPH ( $\mu$ M) using the colorimetric LPH assay kit (Cayman Chemical; Item No. 705002) according to manufacturer's instructions. **4-HNE Assay:** Late-stage lipid peroxidation will be assessed by measuring 4-HNE (fmol/ $\mu$ g) (Cell Biolabs, Inc.; STA-338), which will be quantified using a standard sandwich ELISA designed to detect protein adducts formed via 4-HNE Michael Addition to lysine, histidine, or cysteine residues. **8-ISO Assay:** Late-stage lipid peroxidation will be evaluated by measuring 8-ISO (pg/mL) (Cayman Chemical; Item No. 516351), which will be quantified with a standard competitive sandwich ELISA using an 8-ISO-acetylcholinesterase conjugate as a tracer and 8-ISO-specific rabbit antiserum. The sensitivity and intra- and inter-assay coefficient of variation (CV) of these assays have been validated and published previously. **Oxylipins:** Oxylipin species will be assayed by ultra-high-pressure liquid chromatography tandem mass spectrometry. **MPO assay:** MPO concentrations in blood (pg/mL) will be measured using ELISA. **Ccf-mtDNA:** Mitochondrial dysfunction will be assessed by ccf-mtDNA concentrations, which will be measured using quantitative polymerase chain reaction from circulating cell free DNA purified by commercially available spin columns. **PIGF:** We will measure levels of PIGF using a standard sandwich ELISA. Blood will also be collected at baseline and analyzed for the APOE genotype. Blood cells will be frozen separately for determination of APOE genotype. ApoE genotype will be determined by a polymerase chain reaction based assay at Sunnybrook.

## 7.4 Statistical Analyses

All analyses will be performed using current versions of SPSS and SAS (SAS Institute, Cary, NC, USA). The intention-to-treat analyses will be based on data from all patients who undergo randomization, meet the inclusion criteria for the study, receive the trial medication at least once, and undergo at least baseline observation. Descriptive statistics will be calculated for composite z-scores for executive function, memory, and speed of processing. Categorical variables will be summarized using counts and percentages. Continuous variables will be compared between groups using two sample two sided t-tests (or Wilcoxon rank sum tests for non-normal data), whereas categorical variables will be compared between groups using chi-square analyses or Fisher's exact tests.

Primary Hypothesis: Differences in executive function composite z scores between the groups at 24 weeks will be compared between treatment groups using a two sample two sided t-test. A linear mixed model will be run to compare the rate of change in the executive function measure over time (baseline, 12- and 24-weeks). The linear mixed model is selected as it can accommodate missing data in subjects. The effects of age, sex, BMI, total years of education, VO2 peak, physical activity levels, serum homocysteine, will be included as possible covariates. The same analyses will be repeated with the composite z-scores of the other cognitive domains as repeated variables to test for the effect of NAC treatment on the secondary outcome measures.

Secondary Hypotheses: A linear mixed model will also be used to test the hypothesis that patients with mild VCI treated with NAC will show a greater reduction in 8-ISO/LPH ratio over 24 weeks of treatment. The early to late stage lipid peroxidation marker ratio will be inputted as the repeated variable, and treatment group will be added as a fixed factor. The effects of group by time interaction will be evaluated to indicate significant effects of NAC in reducing oxidative stress markers as compared to placebo. APOE4 genotype status, BMI, VO2 peak, and sex will be added as covariates. Similar analyses will be conducted separately with GPx, GR and GST inputted as the repeated variable. Logistic regression analyses will be performed to examine whether baseline severity of WMH is a significant predictor of cognitive response to NAC treatment at 24 weeks, adjusting for the same covariates.

Exploratory Hypothesis:

A linear mixed model will be used to assess baseline brain GSH as a predictor of change in executive function, processing speed, memory and working memory composite z scores over 24 weeks in patients with mild VCI. A GSH x time interaction will indicate a significant relationship between brain GSH and change in executive function, processing speed, memory and working memory performance over time.

Post-hoc analyses will be used to assess change in 8-ISO/LPH ratio over 24 weeks of treatment between possible and probable mild VCI subgroups using linear mixed models. Between group differences in baseline brain GSH levels will also be assessed using analyses of covariance. Where possible, the primary and secondary hypotheses will also be tested in the probable and possible mild VCI subgroups and compared.

Linear regression will be used to investigate baseline serum S100B as a predictor of baseline brain GSH levels, and if serum S100B at baseline will predict change in brain GSH over a 6-month period. Body fat percentage will be included as a potential confounder in this analysis.

Linear regression will be used to assess association between mitochondrial dysfunction as measured by ccf-mtDNA and oxidative stress markers at baseline and over time. A linear regression model will be used to investigate the association between PIGF, oxidative stress markers at baseline and termination. A linear regression model will be used to investigate peripheral MPO as a predictor of executive function or verbal memory at baseline. Age, use of anti-inflammatory medications and inflammatory and vascular comorbidities will be included as covariates. Measures of mood, cognitive function, and metabolic markers (oxylipins) will be compared between the baseline and follow-up visits, and changes in these measures will be compared between individuals relative to each other in a repeated measures linear regression analyses.

**Safety Outcomes:** Frequency of adverse events between treatment and placebo groups will be compared using chi-square/ Fisher exact tests. In addition, exploratory analyses using logistic regression will be performed to determine predictors of cognitive response to NAC, including demographics and compliance.

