## PROTOCOL SUMMARY

Protocol Title (Short Title)	Efficacy and Safety of N-acetylcysteine in patients with mild vascular cognitive impairment (MOVE-IT)
Protocol Number	1.9
Phase	II
Study Design	Randomized, double-blind, placebo-controlled parallel group
Study Duration	5 years
Setting	Single-centre
Sample Size	60
Main Inclusion Criteria	Males or females aged 55-85 years, with mild vascular cognitive impairment (VCI), who are enrolled in a supervised cardiac rehabilitation program.
Primary Outcome(s):	In patients with mild VCI, those randomized to NAC (2,400 mg/day) will demonstrate greater improvement in executive function over 24 weeks as compared to those randomized to placebo.
Secondary Outcome(s):	In patients with mild VCI, those randomized to NAC (2,400 mg/day) will demonstrate greater improvement in processing speed, memory and working memory over 24 weeks as compared to those randomized to placebo.
Investigational Product and Planned Use	
N-acetylcysteine (NAC) Natural Health Products Directorate (NPN #: 80004844).
 
Patients will be randomized to receive NAC (four 600 mg capsules given as 2 capsules in the morning and 2 capsules in the evening) or matching placebo capsules. The initial NAC dosage will be 600mg/day (one 600mg capsule in the morning) for the first week, followed by 1,200 mg/day (one 600 mg capsule in the morning, one 600mg capsule in the evening) for the second week, followed by 1,800 mg/day (two 600mg capsules in the morning, one 600mg capsule in the evening) for third week, followed by 2,400mg/day (two 600mg capsules in the morning, two 600mg capsules in the evening) for the following 21 weeks.

Statistical Analysis:	Differences in executive function composite z scores between the groups at 24 weeks will be compared between groups using a two sample two sided t-test. A linear mixed model will be run to compare the rate of change in the executive function measure over time.

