### **7.5 Power Calculation**

Based on a published randomized placebo-controlled trial in patients with probable AD, oral NAC treatment resulted in a significant improvement in executive function in the active treatment group ( $p= 0.008$ ) but not in placebo. Our preliminary analysis of MOVE-IT blinded data ( $n=30$ ) was used to provide an updated estimate of the standard deviation ( $SD=0.55$ ) of executive function Z-scores in our population, controlling for education. Based on this, a sample size of 42 (21 in each group) will provide 80% power, at alpha of 0.05, to detect a medium effect size in a linear mixed model with a hypothesized intra-cluster correlation of 0.1. The sample size calculation was carried out using PASS Version 12 (Kaysville, Utah.). Due to the uncertainties of COVID-19 pandemic, a generous drop-out rate was used. To account for a drop-out rate of 42%, we will inflate the sample size to 60.

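### The week-24 t-test leaves out the executive-function score measured before dosing, and the mixed model does not say how baseline is handled; adjusting for baseline costs almost nothing and gains power at moderate to high correlation

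*Combined protocol and SAP*

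**What the plan says.** Two analyses address the primary hypothesis, which concerns improvement in executive function over 24 weeks (section 3.1).

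- **Week-24 comparison, by t-test.** Section 7.4: "Differences in executive function composite z scores between the groups at 24 weeks will be compared between treatment groups using a two sample two sided". The Protocol Summary repeats it: "Differences in executive function composite z scores between the groups at 24 weeks will be compared between groups using a two sample two sided t-test".
- **Mixed model.** Section 7.4: "A linear mixed model will be run to compare the rate of change in the executive function measure over time (baseline, 12- and 24-weeks"). Baseline enters as one of three repeated outcome values. The fixed effects of this model are not written out. The only mixed model in 7.4 with its terms spelled out is the one for the 8-ISO/LPH ratio, which has treatment group as a fixed factor plus a group-by-time interaction.
- **Covariates.** Section 7.4: "The effects of age, sex, BMI, total years of education, VO 2 peak, physical activity levels, serum homocysteine, will be included as possible covariates". The pre-treatment executive-function composite is not listed.
- **Secondary cognitive domains.** Section 7.4: "The same analyses will be repeated with the composite z-scores of the other cognitive domains as repeated variables".
- **Correlation.** Section 7.5 gives the only related figure, planning "to detect a medium effect size in a linear mixed model with a hypothesized intra-cluster correlation of 0.1".

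Appendices A and B both place the cognitive battery at week -5. Section 5.1 uses it for eligibility, so the score should exist for every randomised patient.

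**The concern.** The hypothesis is about improvement, but the week-24 t-test compares final scores and leaves chance differences at baseline in the estimate. With 21 per arm and the SD of 0.55 from section 7.5, that chance difference has standard error 0.55 × √(2/21) = 0.17 z-units. The assumed medium effect is 0.5 × 0.55 = 0.275. (The 0.55 was estimated controlling for education, so the unadjusted figure may differ.)

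The rate-of-change model removes the baseline difference. If baseline means are free by arm, however, it does so by subtraction, which adds the baseline score's own noise when r is low. Each planned analysis is therefore weak over part of the range of r, and the plan gives no evidence on where r lies. In a trial of 60 patients planned on 42 completers, power lost this way can be recovered without extra data.

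**Working it through.** **Inputs.** From section 7.5: 21 per arm, alpha 0.05, SD 0.55, intra-cluster correlation 0.1. From section 7.4: two-sided testing, visits at baseline, 12 and 24 weeks. Assumed: medium means d = 0.5; r, the correlation between visits, is equal for all pairs and ranges from 0.1 to 0.9.

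**The plan's own figure.** Section 7.5 states neither the numerical effect size nor the number of repeated measures, so 42 cannot be reproduced uniquely. For a time-averaged difference, n per arm = 2(1.96 + 0.84)²/d² × [1 + (m − 1) × 0.1]/m. This gives 26 for m = 3 and d = 0.5; 21 for m = 3 and d = 0.55; and 21 for m = 4 and d = 0.5. A time-averaged difference is neither of the analyses in 7.4. With d = 0.5 and r = 0.1, 80% power needs about 64 per arm for the t-test and 114 for the unconstrained slope. That gap is a separate matter; here the three analyses are compared at the planned size.

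**Variance of the treatment contrast, in units of 2 × SD²/n.**

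- Week-24 t-test: 1, with 40 df.
- Slope with free baseline means: 2(1 − r), with 40 df. With visits at 0, 12 and 24 weeks and equal correlations, week 12 gets zero weight, so the contrast is week 24 minus baseline.
- ANCOVA on baseline: (1 − r²) × (1 + 1/38), with 39 df. The second factor, 1 + 1/(N − 4) with N = 42, is the small-sample cost of estimating the baseline slope.

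Power is from the noncentral t with noncentrality 0.5/√(2/21) = 1.620 divided by the square root of the factor. At r = 0.5 the t-test and slope both have noncentrality 1.620, giving 35.3%. The ANCOVA factor is 0.75 × 1.0263 = 0.770, so its noncentrality is 1.847 and its power 43.7%.

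| r | t-test | slope, free baseline | ANCOVA | ANCOVA minus the better of the two |
|---|---|---|---|---|
| 0.1 | 35.3% | 21.8% | 34.8% | −0.5 |
| 0.3 | 35.3% | 26.7% | 37.3% | +2.0 |
| 0.5 | 35.3% | 35.3% | 43.7% | +8.4 |
| 0.6 | 35.3% | 42.4% | 49.6% | +7.2 |
| 0.7 | 35.3% | 53.2% | 58.9% | +5.6 |
| 0.8 | 35.3% | 70.5% | 73.9% | +3.3 |
| 0.9 | 35.3% | 94.2% | 94.7% | +0.5 |

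(Differences in percentage points, taken before rounding.)

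**Break-even.** ANCOVA overtakes the t-test at r of about 0.16 to 0.17 with 21 per arm.

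**Other sizes.** With 30 per arm at r = 0.5, power is 48%, 48% and 59%. The n per arm for 80% power at r = 0.5 is 64, 64 and 49; at r = 0.7 it is 64, 39 and 34.

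**If the mixed model has a common baseline mean.** Assuming a linear treatment effect over time, its slope has relative variance 0.847 at r = 0.1 and 0.727 at r = 0.5. Power is 40% and 46%, no worse than ANCOVA.

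**The case against.** Four points can be made for the plan.

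1. **The t-test is valid.** Under randomisation the chance baseline difference is already in its standard error, and its type I error is correct. A reader might infer bias or an invalid test; the documents do not support that. This stands: the point is efficiency only.
2. **The loss is not universal.** A reader might infer that power is lost at every plausible correlation. The table contradicts this. At 0.1, the only correlation in the documents, the t-test loses nothing, and at 0.9 the slope model loses almost nothing. Against the better of the two planned tests the largest tabulated gain is 8.4 points, and the plan does not say which test decides. This also stands.
3. **The mixed model uses baseline.** A reader might infer that neither analysis does, or that the model is a change-score analysis. Section 7.4 does not write out its fixed effects, and silence about a common baseline mean is not a statement that the means are free. The 8-ISO/LPH model points towards the unconstrained form, but that is inference. What can be said is that the model is under-specified and that the choice matters: 22% or 40% power at r = 0.1.
4. **The governing correlation is unknown.** Reading the intra-cluster correlation of 0.1 as the baseline-to-week-24 correlation is an assumption, and selecting patients on the baseline battery may lower r. This limits any claim about size. It does not favour the planned tests, because a low r is where the change-score form does worst and where ANCOVA costs at most half a point over the range examined.

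**Conclusion.** The point holds as an efficiency improvement, not as an error in the plan. The t-test gives up 2 points of power at r = 0.3, 8 at 0.5, 24 at 0.7 and 39 at 0.8 relative to baseline adjustment. The mixed model, if its baseline means are free, gives up 13 points at r = 0.1, 8 at 0.5 and 3 at 0.8. Over r from 0.1 to 0.9, adjustment is never more than 0.5 point worse than either, and over roughly 0.3 to 0.8 it beats both. Because the plan does not justify a value of r, that robustness is the reason to adopt it.

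The figures rest on 21 completers per arm, d = 0.5, equal correlations between visits, and planned visit times of 0, 12 and 24 weeks with the screening score standing as baseline.

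**What to change.** In section 7.4 and the Protocol Summary:

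- Replace the week-24 t-test with an ANCOVA of the week-24 executive-function composite on treatment and the pre-treatment composite.
- Write out the mixed model. Either give the arms a common baseline mean, or take weeks 12 and 24 as outcomes with the pre-treatment composite and its interaction with visit as covariates. In both cases read the treatment effect at week 24.
- Apply the same specification to processing speed, memory and working memory.

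Extending this to the 8-ISO/LPH, GPx, GR and GST models is optional; no calculation here supports a gain for them.

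The cost is wording and one degree of freedom, with no new data, visits or patients. The ANCOVA is limited to patients with a week-24 score, as the t-test already is; the mixed model with a common baseline mean also keeps those without one. The change should be made before unblinding.

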- In patients with mild VCI, the 8-ISO to LPH ratio will be significantly lower in those receiving NAC supplementation relative to those who received exercise intervention alone

Evidence from neuroimaging studies in VCI patients indicated greater severity and progression of white matter lesion burden was associated with greater declines in executive function and processing speed. We will investigate whether baseline WMH severity significantly predicts the cognitive response to NAC.

- In patients with mild VCI, those with lower WMH volume at baseline will demonstrate greater cognitive improvement in response to 24 weeks of NAC treatment

Previous trials have shown that NAC at these doses is well-tolerated in the elderly. We will investigate tolerability of NAC.

- In patients with mild VCI, measures of safety (including incidences of adverse events and drop-outs) will be comparable between treatment with NAC and placebo.

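### The planned logistic regression on baseline WMH cannot show that response to NAC depends on WMH, because no treatment-by-WMH term, arms, domain or response definition is stated

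*Combined protocol and SAP*

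**What the plan says.** Among the secondary objectives, section 3.2 states that "those with lower WMH volume at baseline will demonstrate greater cognitive improvement in response to 24 weeks of NAC treatment". The rationale given just before is that in VCI "greater severity and progression of white matter lesion burden was associated with greater declines in executive function and processing speed".

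Section 7.4, under the secondary hypotheses, gives the analysis: "Logistic regression analyses will be performed to examine whether baseline severity of WMH is a significant predictor of cognitive response to NAC treatment". The rest of that sentence fixes the time point and points back to a covariate list without naming it: "at 24 weeks, adjusting for the same covariates". The nearest preceding covariate list is the one for the oxidative stress models: APOE4 status, BMI, VO2 peak and sex. The cognitive mixed model has a different list, beginning "The effects of age, sex, BMI, total years of education", which does not include APOE4.

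Three other statements in section 7.4 bear on the point:

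- The general analysis set: "The intention-to-treat analyses will be based on data from all patients who undergo randomization". It is not tied to the WMH model.
- The subgroup plan: "Where possible, the primary and secondary hypotheses will also be tested in the probable and possible mild VCI subgroups and compared".
- A further analysis in the safety paragraph: "exploratory analyses using logistic regression will be performed to determine predictors of cognitive response to NAC". Response is not defined there either.

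Section 7.1 defines the cognitive outcomes only as continuous composite z-scores.

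**The concern.** Both arms take part in cardiac rehabilitation, so a patient's change over 24 weeks mixes the effects of exercise, practice, natural course and, in one arm, NAC. Response to NAC can be identified only against placebo. A claim that it depends on WMH is therefore a claim about a treatment-by-WMH interaction. Section 7.4 names the deciding interaction for the 8-ISO/LPH ratio (group by time) and for brain GSH (GSH by time), but names none here.

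The plan is silent rather than explicit, so three readings are open:

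1. **NAC patients only.** There is no reference arm.
2. **Both arms pooled, no interaction.** The WMH coefficient is an average over arms.
3. **Logistic model with the interaction.** The question is right, but a continuous score has been cut into classes.

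Under the first two, a significant coefficient could be reported as predicting benefit from NAC when it shows only that WMH predicts cognitive change. The protocol's own rationale makes such prognosis plausible. The undefined response also leaves the cut-off, and the choice among four domains, open until the data are seen.

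**Working it through.** The plan gives no sample size, response rate or effect size for this analysis, so there is no figure to reproduce. The check has two parts.

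**What each model estimates.** Let W be standardised baseline WMH, T = 1 for NAC and 0 for placebo, and

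expected change = α + βT − ρW − δTW,

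where ρ is prognosis and δ is effect modification. With equal arms, the WMH slopes on the continuous scale are:

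- NAC only: −(ρ + δ)
- Pooled without interaction: −(ρ + δ/2)
- Treatment-by-WMH term: −δ

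For example, ρ = 0.3 with δ = 0 gives a NAC-only slope of −0.3, and so does ρ = 0 with δ = 0.3. The interaction term separates them (0 against −0.3). The same holds for a binary outcome. In 200,000 simulated patients with WMH prognostic only (log-odds ratio −0.7 per SD), the NAC-only coefficient was −0.70 and the interaction 0.01.

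**Size at this trial's scale.**

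- From section 7.5: 21 per arm (the power target), 30 per arm (60 enrolled), and 60 × (1 − 0.42) = 34.8, about 17 per arm, if the full 42% drop-out occurs.
- Assumed, because the documents do not give them: ρ from 0 to 0.5; total SD of change 1 in the placebo arm; response defined by a median split; four covariates with no effect (APOE4 25%, sex 50%, BMI and VO2 peak normal).
- Method: Wald tests at 5%, with failed fits counted as non-significant. Ordinary least squares on week-24 change stands in for the mixed model's week-24 contrast. There were 3,000 trials per cell (2,000 for NAC-only power).

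WMH prognostic only (δ = 0), share of trials with WMH significant (share of fits failing in brackets):

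| Per arm | Model | ρ = 0 | 0.2 | 0.3 | 0.5 |
|---|---|---|---|---|---|
| 17 | NAC only | 0.3% (24%) | 0.4% (25%) | 0.6% (27%) | 1.8% (32%) |
| 17 | Pooled | 4.7% | 13.5% | 22.7% | 58.4% |
| 21 | NAC only | 1.8% (12%) | 3.0% (12%) | 6.2% (12%) | 12.5% (16%) |
| 21 | Pooled | 4.9% | 15.5% | 30.0% | 70.3% |
| 30 | NAC only | 4.4% (3%) | 11.1% (3%) | 18.9% (3%) | 49.1% (3%) |
| 30 | Pooled | 4.5% | 21.4% | 43.5% | 88.8% |

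The continuous treatment-by-WMH test was significant in 4.4% to 5.7% of trials in every cell. Adding a treatment main effect to the pooled model changed its rates by about one percentage point or less.

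True modification, δ = 0.5 SD per SD of WMH, share significant at ρ = 0.2 / 0.3 / 0.5:

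| Model | 17 per arm | 21 per arm | 30 per arm |
|---|---|---|---|
| NAC-only logistic | 2.7 / 2.8 / 2.7% | 17.4 / 18.5 / 20.0% | 63.3 / 70.7 / 78.1% |
| Logistic with interaction | 9.5 / 5.8 / 2.6% | 13.9 / 11.7 / 5.2% | 24.1 / 21.9 / 13.0% |
| Continuous with interaction | 23.6 / 24.3 / 29.6% | 29.9 / 31.0 / 36.3% | 43.8 / 47.3 / 51.7% |
| Interaction, WMH split in half | 15.5 / 16.7 / 16.5% | 20.5 / 21.3 / 19.9% | 28.6 / 30.3 / 28.4% |

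The NAC-only row is not valid power for modification, because prognosis alone also produces rejections. At 17 per arm, 36% to 52% of those fits failed.

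**Check on a different scale.** Data were generated directly on the log-odds scale (prognostic log-odds ratio −0.5 to −1.0 per SD, no covariates, failed fits dropped). WMH was significant in 10% to 36% (N = 42) and 18% to 59% (N = 60) for NAC only, and in 30% to 78% and 41% to 91% for the pooled model. The interaction was significant in 2% to 4%.

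**The case against.** The strongest reply is that section 3.2 may mean only a comparison of lower with higher WMH among treated patients, which a NAC-only model would match. That reading is possible. Such an analysis can describe who improved while on NAC, but it cannot attribute the difference to NAC. If the team intends no more than that, the hypothesis should say so.

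The prognostic strength is also assumed. The cited association gives no correlation with 24-week change during rehabilitation. At ρ = 0.2 the false signals fall to 0.4% to 11% (NAC only) and 13.5% to 21% (pooled). This stands as a limit on the size, not on the argument.

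The two harms under the NAC-only reading also occur at different sample sizes. At 17 per arm that model rarely shows anything. At 30 per arm it can mislead, but it would then often pick up a true modification as well. Section 7.5 itself calls its drop-out allowance generous, so 17 per arm is the pessimistic end.

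The power figures for the alternative come from a completers' week-24 contrast, not the three-visit mixed model. Under δ = 0.5 the NAC-arm SD is √(1 + 2ρδ + δ²), about 1.20 at ρ = 0.2 and 1.32 at ρ = 0.5. The figures are therefore approximate.

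The intention-to-treat definition does not rescue the plan, because pooling without the interaction still averages prognosis over arms. The probable/possible subgroup comparison keeps the placebo control. However, it is conditional, uses a yes/no MRI category in place of WMH volume, and names no interaction test.

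**Conclusion.** The concern holds. The stated analysis does not answer the stated hypothesis unless a treatment-by-WMH term is added, and no section adds it. Nor are the arms, domain or response definition given anywhere. That conclusion needs no assumed number.

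The size does depend on assumptions. With correlation 0.3 to 0.5 and 21 to 30 per arm, prognosis alone gives a significant WMH coefficient in about 6% to 50% (NAC only) or 30% to 89% (pooled) of trials, against about 5% for the continuous interaction. Under the most favourable reading, a logistic model with the interaction has 3% to 24% power across the sizes considered, against 24% to 52% for the continuous model.

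This is one secondary question in a 60-patient phase II trial. It should be corrected before unblinding, but it does not touch the primary result.

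**What to change.** Replace the WMH sentence in section 7.4 with a short specification:

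- **Model.** Both arms, using the mixed model already planned for the continuous composite z-scores. Add baseline WMH volume and WMH-by-treatment-by-visit with all lower-order terms.
- **WMH scale.** Continuous, with scaling and transformation stated, for example relative to the intracranial volume mask described in section 7.2.
- **Covariates.** List them. Keep baseline APOE4, BMI, VO2 peak and sex, since the cognitive model's list differs.
- **Domains.** Executive function and processing speed, the two that the section 3.2 rationale supports. If both are kept, say which leads.
- **Report.** The week-24 WMH-by-treatment estimate with 95% CI among patients with an MRI, and the number without one.
- **Responder analyses.** Descriptive only, with response defined before unblinding. This should also cover the exploratory predictors of response in the safety paragraph.

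If the team does not wish to claim effect modification, the minimum is to reword the hypothesis as descriptive and to fix the arms, domain and cut-off in advance.

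Sections 5.2 (MRI contraindication excludes) and 7.1 (patients who cannot have an MRI may enrol) must be reconciled, because they decide who has a WMH value.

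The cost is a paragraph of text and no new data. The price is imprecision, which should be stated:

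| | N = 34 | N = 42 | N = 60 |
|---|---|---|---|
| Power, δ = 0.5 SD | 24–30% | 30–36% | 44–52% |
| Power, δ = 0.25 SD | 10–11% | 11–12% | 15–18% |
| 95% CI half-width (SD) | 0.71–0.80 | 0.61–0.69 | 0.49–0.55 |

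If 20% lack an MRI (assumed), power for 0.5 SD is about 20–22%, 24–30% and 35–44% with 28, 34 and 48 patients.
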